10 APPENDIX: CHIA-SOURCED VARIABLE DEFINITIONS AND ABSTRACTION

We will create a subset of cardiac surgery patients using all three CHIA databases to maximize the chance of finding a matching cardiac surgery record in RPDR. UHINs for the cardiac surgery cases are identified in the inpatient database where at least one of 15 procedure codes or principal procedure contains an ICD9-CM code for cardiac surgery (3610-3619). The following lists the minimum set of fields needed to complete the merge.

- a. MDPHHospNum: MDPH hospital number determined from all hospital IDs in the case mix data
- b. AdmitDt: Admission date to hospital
- c. ProcDates: Possible dates for cardiac surgical procedure (15 in inpatient, 3 in OOR data)
- d. ProcedureCodes: ICD-9-CM and CPT (OOR only) codes for cardiac surgery records (only 3 ICD-9-CM in OOR data)
- e. PrincipalProcDate: Date for principal procedure (OOR only)
- f. PrincipalProcedure: ICD9-CM code for PCI and CABG records
- g. Diagnosis Codes: Diagnosis and DRG codes for conditions
- h. DischDate: Discharge date from hospital
- i. RecordType20ID: CHIA Record Id Control Number
- j. UHIN Unique patient identifier from CHIA
- k. DOB: Patient date of birth submitted by hospital
- l. MedicalRecordNum: Hospital patient medical record number
- m. Gender: Patient gender

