1.1 Study Introduction

Briefly, this study examines the occurrence and neurological consequences of atrial fibrillation, occurring after discharge to home or rehab after cardiac surgery. The study examines patients who underwent cardiac surgery at Cardiac Surgical Programs in Massachusetts between 1/1/2012 and 12/31/2016, with a follow-up period that extends to 12/31/2017.

Detailed data will be obtained from individual Programs that encompasses preoperative medical history, the operative period including details about the operation and also the post-operative period until discharge from hospital. Information about the post-hospital discharge course for individual patients will be obtained from the Massachusetts Center for Health Information and Analysis (CHIA) (<https://www.mass.gov/orgs/center-for-health-information-and-analysis>). CHIA collects detailed financial and patient-level data from Massachusetts payers and providers, and makes it available to researchers.

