2 STUDY SUMMARY AND AIMS

The purpose of this study is to determine the incidence, risk factors and adverse events consequent upon atrial fibrillation after cardiac surgery, as well as the association between prior atrial fibrillation and postoperative atrial fibrillation. The study uses information from local Cardiac Surgical Programs to describe the preoperative medical state and immediate post-operative state. Additionally, information from the post-discharge period will be provided by CHIA, by matching the two sources of information using HIPAA-waived data such as medical record number, date of birth, gender and last name. Once matched, the data are stripped of identifiers.

2.1 Study Design:

We will employ a retrospective cohort design, examining patients who underwent cardiac surgery at Cardiac Surgical Programs in Massachusetts between 1/1/2012 and 12/31/2016, with a follow-up period that extends to 12/31/2017. The study examines the risk factors and incidence of post-operative atrial fibrillation, stroke and other focal neurological events after discharge from hospital.

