5 DATA SOURCES

6 STUDY POPULATIONS

6.1 Inclusion Criteria

Inclusion criteria for this study are patients who undergo surgical procedures that include coronary artery bypass graft surgery, aortic valve surgery or mitral valve surgery and other valvular surgical procedures.

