63	Prior other valve surgery	CSP	PrValveProc1, PrValveProc2, PrevProcAVReplace , PrevProcAVRepair , PrevProcTVReplace , PrevProcTVRepair , PrevProcPV , PrevProcAVBall , PrevProcMVBall , PrevProcTCVRep , PrevProcPercVRepair
64	Other cardiac surgery	CSP	PrOthCar, PrOthCongen, POC, POCInt1, POCInt2, POCInt3
65	Prior ICD placement	CSP	PrOCAICD
66	Prior pacemaker placement	CSP	PrOCPace
67	Prior arrhythmia surgery	CSP	POArr
69			
70	Preoperative laboratory testing		
77	White cell count (10^6 /dL)	CSP	WBC
78	Creatinine (mg/dL)	CSP	CreatLst
79			
80	Preoperative Cardiac Imaging		
81	Number of diseased coronary vessels	CSP	NumDisV
82	0		
83	1		
82	2		
83	≥ 3		
84	LV Ejection fraction	CSP	HDEF
85	<30%		
86	30-54%		
87	$\geq 55\%$		
88	Aortic stenosis	CSP	VDStenA
89	Aortic insufficiency	CSP	VDInsufA
90	Mitral stenosis	CSP	VDStenM
91	Mitral insufficiency	CSP	VDInsufM
92	Tricuspid valve disease	CSP	VDStenT, VDStenP
93	Pulmonary valve disease	CSP	VDStenP, VDInsufP

94

95 **Surgery**

[figure not shown]
96	Year of operation	CSP	SurgDt
97		2012	
98		2013	
99		2014	
100		2015	
101		2016	
101	CABG surgery	CSP	OpCAB
102	Number of conduits placed	CSP	DistArt + DistVein
103		1	
104		2	
105		>=3	
106	AVR surgery	CSP	VSAVPr, VSAV
107	MVR surgery	CSP	OpMitral, VSMVPr, VSMV
108	Other valve surgery	CSP	OpPulm, VSPV, OpTricus, VSTV
109	Ascending aortic surgery	CSP	AortProcTotArch, ONCArch, AortProcHemi, AortProc , OpAortic, OCAoProcType, AortProcRoot, ONCAoRt, AortProcAsc, ONCAsc, ONCAsc
110	Other non-CABG, non valvular surgery	CSP	OpOCard
111	Atrial septal surgery	CSP	OCarASD, OCarASDPFO
114	Ventricular outflow tract surgery	CSP	OCarSubaStenRes , ResectSubA
115	Congenital heart surgery		OCarCong , OCarCongProc1 , OCarCongProc2 , OCarCongProc3
116	Carotid endarterectomy	CSP	
117	Reoperation	CSP	Incidenc
118	Surgical urgency	CSP	Status
119		Elective	
120		Urgent	
121		Emergent	
122	Postoperative duration (days)	CSP	DischDt - SurgDt
123			
124	Post-operative complications		

125	Stroke	CSP and CHIA	CNSTrokP
126	TIA	CSP and CHIA	CNSTrokTTIA
127	Atrial fibrillation	CSP and CHIA	COAtFib
128	Reoperation for bleeding	CSP and CHIA	COpReBld
129	Pacemaker inserted	CSP and CHIA	CRythmDis
130	In-hospital atrial fibrillation	CSP	COAtFib
131	In-hospital atrial flutter	CSP	
132			
133	Discharge medications and devices		
134	Aspirin	CSP and CHIA	DCASA
135	Warfarin	CSP and CHIA	DCCoum
136	Anti-platelet agent	CHIA	-
137	Beta blocker	CSP and CHIA	DCBeta
138	Amiodarone	CSP and CHIA	DCAmiodarone

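### The only CHIA case-finding rule is ICD-9-CM block 3610-3619; run as written, it misses eligible valve surgery without bypass unless another inpatient record carries a code in that block

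*Combined protocol and SAP*

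**What the plan says.** Appendix 10 builds a CHIA subset of surgical patients. A patient's CHIA identifier is picked up from the inpatient database "where at least one of 15 procedure codes or principal procedure contains an ICD9-CM code for cardiac surgery (3610-3619"). No other range of procedure codes appears in the plan. The same appendix lists the fields needed for the merge, including "PrincipalProcedure: ICD9-CM code for PCI and CABG records" (item f), "UHIN Unique patient identifier from CHIA" (item j) and "MedicalRecordNum: Hospital patient medical record number" (item l).

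Section 6.1 admits "coronary artery bypass graft surgery, aortic valve surgery or mitral valve surgery and other valvular surgical procedures". Table 1 has separate rows for AVR, MVR and "other valve surgery". Figure 1 ends in three strata: CABG only, AVR with or without CABG, and MVR with or without AVR or CABG.

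On data flow, Section 1.1 states: "Information about the post-hospital discharge course for individual patients will be obtained from the Massachusetts Center for Health Information and Analysis (CHIA"). Section 2 describes the linkage as done "by matching the two sources of information using HIPAA-waived data such as medical record number, date of birth, gender and last name" and mentions no filter on procedure codes.

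**The concern.** The case-finding rule and the eligibility rule describe different populations. The plan labels 3610-3619 only as cardiac surgery. In the standard meaning of the printed codes the block is coronary bypass and holds no valve procedures. Item f fits that reading, since it describes the principal-procedure field in terms of PCI and CABG and does not mention valves.

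Both primary aims concern events after discharge, and those events come from CHIA. A patient outside the CHIA subset would be removed at the matching step in Figure 1. The AVR and MVR strata would then hold combined valve-plus-bypass operations, plus only those valve-only patients who have a bypass code on another record. The results would be presented as describing the Section 6.1 population but would not do so.

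The missing group is not incidental. Section 1.2 links AF, the main exposure, with mitral and other valvular disease. It also names coronary disease, and the plan gives no split of prior AF by operation, so the direction of any bias cannot be stated.

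**Working it through.** **1. The passages side by side**

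| Point | Where | Content |
|---|---|---|
| Eligible operations | Section 6.1 | Bypass, aortic, mitral and other valve surgery |
| Planned strata | Figure 1 | AVR and MVR, each with or without CABG |
| CHIA selection | Appendix 10 | Inpatient record with a code in 3610-3619; no other range |
| Unit of selection | Appendix 10, item j | Patient identifier, so any qualifying inpatient record brings the patient in |
| Timed post-discharge AF | Table 1, rows 142-149 | CHIA only |
| Timed post-discharge stroke | Table 1, rows 152-160 | CHIA only |
| Site-file alternative | Appendix 9, lines 204-205 | Readmission flag and reason; no readmission date and no STS 2.81 field number |

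Neither of two other features of Appendix 10 adds a selection route. The reference to three CHIA databases states the aim of the subset. The CPT codes for OOR data stand in the list of merge fields.

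It follows that a valve-only patient with no code in the block on any inpatient record is eligible, is not selected, and has no timed source for either primary outcome.

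**2. The plan's own power figure**

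Inputs from Section 4: 4,000 patients with prior AF and 46,000 without, two-sided 0.05, 80% power, 25% comparator rate.

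- h = (1.9600 + 0.8416) × √(1/4,000 + 1/46,000) = 0.0462. The plan states 0.046.
- Difference from 25% = sin²(asin√0.25 + h/2) − 0.25 = 2.03 points. The plan states 2%.

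The plan's figure reproduces.

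**3. Illustration of the loss**

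Two inputs are assumed because the documents give neither: the valve-only share s (20-40%) and the fraction e of those patients with a qualifying code on another inpatient record (0-10%). The 50,000 is the estimate in Section 2.2.

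Not selected = 50,000 × s × (1 − e). With N patients kept and 8% prior AF among them, h = 2.8016 × √(1/(0.08N) + 1/(0.92N)).

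| s | e | Not selected | N kept | h | Detectable difference (points) |
|---|---|---|---|---|---|
| – | – | 0 | 50,000 | 0.0462 | 2.03 |
| 0.20 | 0.10 | 9,000 | 41,000 | 0.0510 | 2.24 |
| 0.20 | 0 | 10,000 | 40,000 | 0.0516 | 2.27 |
| 0.40 | 0.10 | 18,000 | 32,000 | 0.0577 | 2.54 |
| 0.40 | 0 | 20,000 | 30,000 | 0.0596 | 2.62 |

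The 8% is itself an assumption. Suppose instead that prior AF is 12% among those lost, with e = 0:

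- 10,000 lost: 4,000 − 1,200 = 2,800 with prior AF against 37,200 without; h = 0.0549, or 2.41 points.
- 20,000 lost: 4,000 − 2,400 = 1,600 against 28,400; h = 0.0720, or 3.18 points.

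**The case against.** The strongest reply has four parts.

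- **The meaning of the codes is not in the plan.** No section says that 3610-3619 is bypass only, and item f is weak support because it names PCI, which is not an eligible operation. This stands as a caveat. The reading rests on the standard classification of codes that the plan itself prints. Even without it, nothing in the plan shows that one block covers the valve operations it studies.
- **Appendix 10 may not govern.** It refers to a match in RPDR, a source named nowhere else. Figure 1 starts from local STS databases, the Appendix 11 timeline places submission and merging at CHIA, and Section 2 links by identifiers alone. Items k, l and m repeat three of those identifiers (date of birth, medical record number, gender), so the two descriptions could be successive steps or alternatives. This also stands: the loss is conditional. But the plan does not say which text applies, and only Appendix 10 sets out a case-finding rule.
- **A large loss would be seen.** Figure 1 counts exclusions at matching and Table 1 counts valve operations. That might reveal the problem but would not repair it. Figure 1 splits by operation only after exclusions, so it would not show match rates by type.
- **The size is assumed.** Correct. The headcount and power figures are illustrations, and the range widens if prior AF is commoner among those lost.

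**Conclusion.** The concern holds. As written, the CHIA selection rule does not cover the Section 6.1 population, and both primary analyses depend on CHIA for timed outcomes. This must be fixed before the extraction is relied on, because modelling cannot recover patients who were never linked.

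The conclusion rests on two conditions: that Appendix 10 governs the linkage, and that 3610-3619 carries its standard meaning. A program that in practice uses a wider code list would avoid the loss, but the plan does not describe one. Neither the number lost nor the direction of bias can be derived from the documents. The loss of power is secondary; the main effect is on which patients are analysed. Confidence is medium because of these conditions.

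**What to change.** 1. In Appendix 10, replace the single block with the procedure codes for every Section 6.1 operation: bypass plus aortic, mitral, tricuspid and pulmonic valve procedures. Alternatively, link from the site STS records using the Section 2 identifiers, with no procedure-code filter beforehand.
2. State whether Section 2 or Appendix 10 governs the linkage or, if they are successive steps, their order. Reconcile the RPDR reference and item f with the rest of the plan.
3. Report match rates by operation type in Figure 1.

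The cost is a longer code list, or no pre-filter, in the CHIA query, and a sentence on linkage. No new data source is needed. The query has to be repeated only if extraction has already been done, which the documents do not say.

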11 APPENDIX: PROPOSED TIMELINE

Activity	Jan-Feb 2018	Feb-Mar 2018	Apr-May 2018	May-Jul 2018	Jul-Sep 2018	Sep-Oct 2018	Oct-Nov 2018
Study design							
IRB and DUA approval							
Data submission and merging at CHIA							
Data cleaning and analysis							
Analysis write-up and first circulation							
Paper preparation and second circulation							
Paper submission							

12 APPENDIX: SHELL TABLES AND FIGURES

12.1 Tables

Table 1: Characteristics of the study participants.

Table 2: Comparison of characteristics of patients with post-discharge atrial fibrillation and those patients who did not have post-discharge atrial fibrillation

Table 3: Time-adjusted risk of post-discharge atrial fibrillation

Table 4: Time-adjusted risk of post-discharge stroke

Table 5: Time-adjusted risk of post-discharge mortality

12.2 Figures

Figure 1: CONSORT diagram

Figure 2: Time course of the occurrence of post-discharge AF

Figure 3: Time course of the occurrence of post-discharge stroke stratified by occurrence of post-discharge AF

Figure 4: Time course of the occurrence of post-discharge mortality stratified by occurrence of post-discharge AF

Table 1: Characteristics of the study participants. Data are reported as number and percentage, or median and 10-90% quantiles, as appropriate

CSP = Cardiac surgical program

CHIA = Center for Health Information and Analysis

	Patient characteristic	Data source	Source variable
0	Demographics		
1	Age at surgery (years; N/%)	CSP	Calculated
2	<50		SurgDt - DOB
3	50-59		
4	60-69		
5	70-79		
6	≥80		
7	Gender (Male; N/%)	CSP	Gender
8	Race (Caucasian; N/%)	CSP	RaceCaucasian
9	Ethnicity	CSP	Ethnicity
10	Height (cm; mean/SD)	CSP	HeightCm
11	Weight (kg; mean/SD)	CSP	WeightKg
12	BMI (kg/m ² ; N/%)	CSP	Calculated
13	<20		
14	20-24.9		
15	25-29.9		
16	30-34.9		
17	≥35		
18	Payor		
19	Government	CSP	PayorGov
20	Commercial	CSP	PayorComm
21	HMO	CSP	PayorHMO
22	Prior Medical History		
23	Atrial fibrillation	CSP and CHIA	ArrhythAFib, ArrythAFibDur, ArrythAFibTy
24	Atrial flutter	CSP and CHIA	ArrhythAFlutter
25	History of arrhythmia	CSP and CHIA	
26	Heart block or sick sinus syndrome	CSP and CHIA	ArrhyVtachSicSinSyn, ArrhyTHB, ArrhyVtachHrtBlk, ArrhythSSS

27	VT/VF	CSP and CHIA	ArrhyVtach, ArrhythVV
28	Smoker past or current	CSP	TobaccoUse, CigSmoker, SmokCurr
29	COPD	CSP	ChrLungD
30	Diabetes	CSP	Diabetes, DiabCtrl
31		NIDDM	
32		IDDM	
33	Dyslipidemia	CSP	Dyslip
35	Dialysis	CSP	Dialysis
36	Hypertension	CSP	Hypertn
37	Peripheral vascular disease	CSP	PVD
38	Sleep apnea	CSP	SlpApn
39	Alcohol use	CSP	Alcohol
40	Cerebrovascular disease	CSP	CVD
41	Prior CVA	CSP	CVA, CVAWhen
42	TIA	CSP	CVDTIA
43	Carotid Stenosis	CSP	CVDCarSten
44	Prior carotid surgery	CSP	CVDPCarSurg
45			
46	Medications		
47	ACEI/ARB	CSP	MedACEI48
48	Anticoagulant or anti-platelet drug	CSP	MedACoag
49	Amiodarone	CSP	MedAmiodarone
50	Aspirin	CSP	MEDASA
51	Beta blocker	CSP	MedBeta
52	Calcium channel blocker	CSP	MedCChanTher
53	Antiarrhythmic	CSP	MedAarry
54	Coumadin	CSP	MedCoum
55			
56	Prior Cardiac Status		
57	Heart failure		PriorHF
58	Prior MI		PrevMI, MIWhen
59		Past	
60		Recent	
61	Prior CABG surgery	CSP	PrCAB

62	Prior mitral valve surgery	CSP	PrValveProc1, PrValveProc2, PrevProcMVReplace, PreProcMVRRepair
63	Prior other valve surgery	CSP	PrValveProc1, PrValveProc2, PrevProcAVReplace , PrevProcAVRepair , PrevProcTVReplace , PrevProcTVRepair , PrevProcPV , PrevProcAVBall , PrevProcMVBall , PrevProcTCVRep , PrevProcPercVRepair
64	Other cardiac surgery	CSP	PrOthCar, PrOthCongen, POC, POCInt1, POCInt2, POCInt3
65	Prior ICD placement	CSP	PrOCAICD
66	Prior pacemaker placement	CSP	PrOCPace
67	Prior arrhythmia surgery	CSP	POArr
69			
70	Preoperative laboratory testing		
77	White cell count (10^6 /dL)	CSP	WBC
78	Creatinine (mg/dL)	CSP	CreatLst
79			
80	Preoperative Cardiac Imaging		
81	Number of diseased coronary vessels	CSP	NumDisV
82	0		
83	1		
82	2		
83	≥ 3		
84	LV Ejection fraction	CSP	HDEF
85	<30%		
86	30-54%		
87	$\geq 55\%$		
88	Aortic stenosis	CSP	VDStenA
89	Aortic insufficiency	CSP	VDInsufA
90	Mitral stenosis	CSP	VDStenM
91	Mitral insufficiency	CSP	VDInsufM
92	Tricuspid valve disease	CSP	VDStenT, VDStenP
93	Pulmonary valve disease	CSP	VDStenP, VDInsufP

94

95 **Surgery**

[figure not shown]
96	Year of operation	CSP	SurgDt
97		2012	
98		2013	
99		2014	
100		2015	
101		2016	
101	CABG surgery	CSP	OpCAB
102	Number of conduits placed	CSP	DistArt + DistVein
103		1	
104		2	
105		>=3	
106	AVR surgery	CSP	VSAVPr, VSAV
107	MVR surgery	CSP	OpMitral, VSMVPr, VSMV
108	Other valve surgery	CSP	OpPulm, VSPV, OpTricus, VSTV
109	Ascending aortic surgery	CSP	AortProcTotArch, ONCArch, AortProcHemi, AortProc , OpAortic, OCAoProcType, AortProcRoot, ONCAoRt, AortProcAsc, ONCAsc, ONCAsc
110	Other non-CABG, non valvular surgery	CSP	OpOCard
111	Atrial septal surgery	CSP	OCarASD, OCarASDPFO
114	Ventricular outflow tract surgery	CSP	OCarSubaStenRes , ResectSubA
115	Congenital heart surgery		OCarCong , OCarCongProc1 , OCarCongProc2 , OCarCongProc3
116	Carotid endarterectomy	CSP	
117	Reoperation	CSP	Incidenc
118	Surgical urgency	CSP	Status
119		Elective	
120		Urgent	
121		Emergent	
122	Postoperative duration (days)	CSP	DischDt - SurgDt
123			
124	Post-operative complications		

125	Stroke	CSP and CHIA	CNSTrokP
126	TIA	CSP and CHIA	CNSTrokTTIA
127	Atrial fibrillation	CSP and CHIA	COAtFib
128	Reoperation for bleeding	CSP and CHIA	COpReBld
129	Pacemaker inserted	CSP and CHIA	CRythmDis
130	In-hospital atrial fibrillation	CSP	COAtFib
131	In-hospital atrial flutter	CSP	
132			
133	Discharge medications and devices		
134	Aspirin	CSP and CHIA	DCASA
135	Warfarin	CSP and CHIA	DCCoum
136	Anti-platelet agent	CHIA	-
137	Beta blocker	CSP and CHIA	DCBeta
138	Amiodarone	CSP and CHIA	DCAmiodarone
139			
140	Post-discharge atrial fibrillation		
141	Discharged in AF	CSP	
142	1 - 30 days	CHIA	
143	31 - 90 days	CHIA	
144	91 - 182 days	CHIA	
145	183 - 365 days	CHIA	
146	1 - 2 years	CHIA	
147	2 - 3 years	CHIA	
148	3 - 4 years	CHIA	
149	4 - 5 years	CHIA	
150			
151	Post-discharge stroke		
152	1 - 30 days	CHIA	
154	31 - 90 days	CHIA	
155	91 - 182 days	CHIA	
156	183 - 365 days	CHIA	
157	1 - 2 years	CHIA	
158	2 - 3 years	CHIA	
159	3 - 4 years	CHIA	

160	4 – 5 years	CHIA
161		
162	Mortality	
163	30-day mortality	CSP
164	1-year mortality	CSP
165	5-year mortality	CSP

Table 2: Comparison of characteristics of patients with post-discharge atrial fibrillation and those patients who did not have post-discharge atrial fibrillation

Figure 1: CONSORT Diagram.

Patients reported in local STS databases (N = xx,xxx)

Operations reported local STS databases (N = xx,xxx)

Excluded after matching

- x,xxx patients
- x,xxx operations

Patients reported remaining after matching (N = xx,xxx)

Operations reported remaining after matching (N = xx,xxx)

Excluded after data review (N=x,xxx)

- Inclusion criterion not present
- Exclusion criterion present
- Covariate data not present
- Missing outcome

Eligible patients (N = xx,xxx)

CABG-only surgery (N = xx,xxx)

AVR +/- CABG surgery (N = xx,xxx)

MVR +/- AVR +/- CABG surgery (N = xx,xxx)

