3 STUDY ENDPOINTS AND COVARIATES

3.1 Definitions of Study Endpoints

1. Postoperative atrial fibrillation occurring after discharge from hospital
2. Stroke or other focal neurologic event occurring after discharge from hospital
3. All-cause mortality
4. Stroke-related mortality

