3.3 Modifications or derivations of standard variables

Hospital admissions will be defined using continuous in-patient stays (CIS) which combine data from each event within hospital, which includes within hospital transfers. Diagnostic subgroups will be defined using the code recorded for the main diagnosis for the first event within a CIS. The ninth

International Classification of Disease codes (ICD-9) codes will be used to define the specific conditions of interest.

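### Figures 3 and 4 split stroke and death curves by AF that arises during follow-up, with no AF-timing rule; drawn as ever/never AF, Figure 4 carries immortal time and Figure 3 mixes event order

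*Combined protocol and SAP*

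**What the plan says.** Section 12.2 lists "Figure 3: Time course of the occurrence of post-discharge stroke stratified by occurrence of post-discharge AF" and "Figure 4: Time course of the occurrence of post-discharge mortality stratified by occurrence of post-discharge AF". Section 3.1 names the stratifier as the first study endpoint: "Postoperative atrial fibrillation occurring after discharge from hospital". The Table 1 shell counts it from CHIA in bins running from 1-30 days to 4-5 years, the same period in which strokes and deaths accrue. The first row under that heading, "Discharged in AF", is known at time zero, but the plan does not say whether it counts in the figures' AF stratum.

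No section says how the curves are drawn. The time-varying terms in section 7.1.1 serve only to check proportional hazards. The nearest guide is Table 2, an ever/never split: "Comparison of characteristics of patients with post-discharge atrial fibrillation and those patients who did not have post-discharge atrial fibrillation". Titles such as "Table 5: Time-adjusted risk of post-discharge mortality" do not define the time adjustment or name an exposure.

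The source of the AF date is also open. Section 10 lists "Diagnosis Codes: Diagnosis and DRG codes for conditions" among the CHIA fields, while section 3.3 says "Diagnostic subgroups will be defined using the code recorded for the main diagnosis for the first event within a CIS". Neither states which identifies post-discharge AF.

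**The concern.** A curve that starts at discharge should be split by something known at discharge. If it is split by whether AF ever occurs, group membership depends on the future.

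- **Figure 4.** A patient can enter the AF stratum only by living to the AF date. The time before AF is death-free by construction, and every death before AF goes to the no-AF stratum. This makes AF look protective. AF first coded at the admission that ends in death works the other way.
- **Figure 3.** This is not strictly immortal time, because a non-fatal stroke does not prevent later AF. The fault is order: strokes before AF, and AF first found at the stroke admission, are credited to AF.

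Sections 1.1 and 2 present the study as one of the consequences of AF after surgery. Figures 3 and 4 are the only outputs that explicitly link post-discharge AF to stroke or death, so readers will compare the two curves. Drawn ever/never, they can show a gap where there is no effect, or hide or reverse a real one.

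**Working it through.** **The plan's own figure.** The plan gives no number for these figures. Its one computed design figure (section 4) reproduces: (1.960 + 0.842) × √(1/4,000 + 1/46,000) = 2.802 × 0.01648 = 0.0462, against 0.046 stated. It concerns prior AF and does not bear on this point.

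**Inputs from the plan.** Follow-up of about 1-6 years (surgery 2012-2016, follow-up to the end of 2017; sections 1.1 and 2.1). 50,000 patients, and 25% AF (section 4, where it refers to postoperative AF in patients without prior AF).

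**Assumptions.** Death 4% per year and stroke 1% per year. AF onset even over follow-up, half within 90 days, or 80% within 90 days. The share of events at which AF is first coded is varied. AF raises risk only after its date.

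**Figure 4, by hand.** Let the death rate λ be the same for everyone, f the share of the ever-AF stratum's follow-up that precedes AF, and r the ratio of total follow-up, ever-AF to never-AF.

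- AF stratum rate: λ(1 − f)
- No-AF stratum rate: λ(1 + f·r), because it receives all deaths that occur before AF
- Apparent ratio under the null: (1 − f)/(1 + f·r)

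Simulation gives f = 0.47 / 0.30 / 0.15 for the three onset patterns. If mean follow-up were equal, r = 25/75 = 1/3:

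- Even: 0.53/1.157 = 0.46
- Half early: 0.70/1.10 = 0.64
- 80% early: 0.85/1.05 = 0.81

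**Figure 4, by simulation** (ever/never hazard ratio):

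| Setting | Even | Half by 90 d | 80% by 90 d |
|---|---|---|---|
| True 1.0, no terminal coding | 0.44 | 0.63 | 0.82 |
| True 2.0, no terminal coding | 0.85 | 1.23 | 1.59 |
| True 1.0, 10% of no-AF deaths first coded AF at the fatal admission | 0.74 | 0.96 | 1.18 |
| Same, 20% | 1.08 | 1.36 | 1.62 |
| Share at which the bias changes sign | 18% | 11% | 5% |

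The hand formula lands close to the first row. The remaining gap in the even pattern arises because ever-AF patients are observed longer.

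**A timing figure from the plan.** Section 1.2 cites continuous-monitoring data with AF in 60% overall and 39% beyond 3 months. So at least (60 − 39)/60 = 35% of those with AF had it first within 3 months. With 35% early and no terminal coding, a true 1.0 shows as 0.55, a true 1.5 as 0.82 and a true 2.0 as 1.09.

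**Sensitivity to the AF definition.** If 25% means AF by 5 years rather than AF observed during follow-up, the null is 0.46-0.47 / 0.72-0.74 / 0.86-0.88 for death rates of 2-6% per year. A true 2.0 at 4% per year shows as 0.89 / 1.44 / 1.73. With AF incidence from 3% to 60% (section 1.2), the null runs from 0.39 to 0.90.

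**Figure 3, ever/never.** With no stroke-triggered AF detection, the null stays at 0.99-1.00, but 47% / 30% / 15% of strokes in the AF stratum precede AF, and a true 2.0 shows as 1.5-1.9. If 10% of strokes without earlier AF reveal AF, the null is about 1.4 and a true 2.0 shows as 1.9-2.4. At 20% the null is 1.8-1.9 and a true 2.0 shows as 2.5-3.0. If 15% of strokes are fatal and none reveal AF, the null is 0.90-0.96.

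**The alternative.** A 90-day landmark returns a mortality null of 1.00-1.03 and a stroke null of 0.99-1.04 at 25% ever AF, over coding shares of 0-20%. Updating AF status over time without an order rule is not enough: with a 10% share, the null is 1.50-1.80 for death and 1.50-1.82 for stroke. With the rule it is 0.99-1.01.

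**The case against.** These are one-line shell titles for descriptive figures. No numbered aim, model, named subgroup or sensitivity analysis uses post-discharge AF as an exposure. That stands, and it limits the weight of the point: the primary Cox models and the section 7.4.3 subgroups rest on prior AF and AF at discharge, both known by discharge.

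The drawing method is unstated, and the titles could also fit a time-updated split. Table 2 is a baseline comparison and does not settle how a time course is drawn. That is fair, and the finding is conditional on the ever/never reading. But that is the plain reading, and nothing in the plan rules it out.

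The most striking numbers need even AF onset, which puts only about 1,100 of 12,500 ever-AF patients (9%) within 90 days and sits badly with section 1.2. This is partly right. At 35% early, a true 2.0 is diluted to 1.09 rather than reversed, though a true 1.5 still reverses. Coded AF may also come later than continuously monitored AF.

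The coding shares have no basis in the plan, and without them Figure 3 shows almost no bias under the null. Also right: what remains in Figure 3 is mislabelled order and dilution of a true effect. Nor is all post-discharge AF learned in follow-up, if patients discharged in AF are counted in the stratum.

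**Conclusion.** The concern holds. The plan splits two time courses by an endpoint that arises during the same follow-up and gives no timing rule. Drawn as ever/never AF, Figure 4 carries immortal time and Figure 3 mixes event order. Without AF coded at the fatal admission, a true null in Figure 4 shows as 0.44-0.82 and a true 2.0 as 0.85-1.59. With such coding the sign can change, so the net direction is uncertain for both figures. The sizes rest on assumed AF timing, event rates and coding shares; the existence of the bias under the ever/never reading does not. This should be fixed before the figures are drawn, but it does not touch the primary analyses.

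**What to change.** Draw Figures 3 and 4 as landmark curves: for example, AF status at 90 days after discharge, among patients alive at 90 days and, for Figure 3, also stroke-free. State whether patients discharged in AF belong to the AF stratum, and whether post-discharge AF comes from the main diagnosis only or from any diagnosis code. If Simon-Makuch curves or a time-dependent Cox model are preferred, count AF first recorded at or after the stroke encounter, or at the terminal admission, as not preceding the event.

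The cost is a few lines of SAP text. The landmark uses event dates the figures already need. The terminal-admission rule also needs admission dates; section 10 lists them for the merge, but section 8.1 says the final analytic data set holds no CHIA case mix fields, so their availability should be confirmed.

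The landmark has a price:

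- It drops events in the first 90 days, about 7-8% under constant hazards and more if risk is front-loaded.
- It dilutes a true mortality ratio of 2.0 to about 1.75-1.95, because later AF stays in the no-AF group.
- Its AF stratum is about 1,100, 6,200 or 10,000 of 50,000 patients for even, half-early and 80%-early onset, out of about 12,500 ever AF.
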